**FORM: Application for Human Research**

| NUMBER | FORM DATE | PAGE |
|--------|-----------|----------|
| F200 | 02/2014 | 31 of 44 |

1039 and gender. Randomization will consist of permuted blocks to achieve balance over time. Repeated
1040 measures analysis of variance (ANOVA) and linear mixed-model approaches will be used for the primary
1041 analyses examining the efficacy of light treatment condition on measures of mood and sleep. Between
1042 group factors will correspond to the two light conditions (BL vs PL) and will control for any baseline
1043 differences in demographic variables and severity scores as appropriate. Based on specific hypotheses,
1044 separate ANOVAs will be performed for each type of dependent variable (e.g., subjective sleep scores,
1045 CAPS-2 symptom scores, mood scores, MRS metabolites). The relationship between these change
1046 indices and sleep variables will be analyzed using correlation and linear regression models in SPSS. Tests
1047 for normality will be conducted for all variables. In the case on non-normality, appropriate data
1048 transformation or non-parametric techniques will be employed (e.g., Kruskal-Wallis or Friedman tests for
1049 ANOVA; Mann-Whitney U or Wilcoxon for 2-group comparisons). Inflation of Type I error will be
1050 controlled first through the use of planned comparisons based on the hypotheses and the use of protected
1051 omnibus F-tests. Post-hoc analyses will be undertaken with protected comparisons (e.g., Tukey) or
1052 Bonferroni adjustment. Functional MRI data will be analyzed using statistical parametric mapping
1053 (SPM8) software, implementing the general linear model to compare pre- to post-therapy changes in
1054 functional responses between the active and placebo groups and across diagnostic groups, and sleep
1055 variables will be tested as covariates in the models. Finally, proton spectroscopy data for each of the
1056 metabolites will be quantified and compared for pre- to post-therapy changes in metabolite concentrations
1057 between the active and placebo treatment groups and across diagnostic groups. Type I error during
1058 neuroimaging will be controlled via whole brain False Discovery Rate (FDR) correction or small volume
1059 corrections using Family Wise Error (FWE) rate within *a priori* specified regions of interest. To handle
1060 missing data, we will first determine the potential cause of the data loss. Statistically, missing data can be
1061 considered as falling into three types: 1) missing completely at random, 2) missing at random, or 3)
1062 missing not at random. The type of missing data will dictate the approach. Assuming type 1, and that the
1063 number of missing values is low, we will use a standard listwise deletion procedure. However, assuming
1064 that a larger number of values is missing, and data are not missing completely at random, we will be able
1065 to apply missing data imputation methods.

1066 **Power Analysis:** A power analysis based on a proposed sample size of 90 subjects suggested that
1067 with an omnibus 2 between-groups (BL vs. PL) x 2 within-subjects (pre- vs post-treatment) mixed design,
1068 assuming a moderate effect size ($f = .25$), and $\alpha = .05$, there should provide be adequate power to detect
1069 most effects. First, the primary hypotheses of the study focus on interaction effects across groups (i.e.,
1070 treatment x session interactions), which will have exceptional power ($1-\beta = 0.99$) to detect a moderate
1071 effect size at $\alpha = .05$ (see Figure 18A). Paired comparisons within each group of will also have excellent
1072 power of .91 to detect moderate effect size changes ($d = .50$), with 2-tailed tests (see Figure 18B).
1073 Without regard to group differences, a sample size of 90 would yield power = 0.84 to detect a moderate
1074 linear association (i.e., $r \geq .30$) between a predictor variable (e.g., average sleep; change in sleep
1075 parameters, PTSD symptom severity; neurocognitive performance; etc.) and an outcome variable (e.g.,
1076 fMRI signal intensity changes; spectroscopic metabolite changes; etc.), with a two-tailed test at $\alpha = .05$
1077 (see Figure 16). Thus, the proposed sample size of $n = 45$ per group appears to provide adequate power
1078 for testing the major hypotheses of the proposed study.

FORM: Application for Human Research

| NUMBER | FORM DATE | PAGE |
|---------------|------------------|-------------|
| F200 | 02/2014 | 32 of 44 |

1079 **Functional Image Pre-Processing:** Functional neuroimaging data will be preprocessed in SPM8
1080 [123]. Following standard algorithms, functional images will be slice-time corrected, co-registered to
1081 their anatomical T1-weighted images, realigned, unwarped to correct for field inhomogeneity, normalized
1082 to the standard three-dimensional space of the Montreal Neurological Institute (MNI), spatially smoothed
1083 using an isotropic Gaussian kernel (full width half maximum [FWHM] = 6 mm), and resliced to 2x2x2
1084 mm isotropic voxels using sinc interpolation. Depending on the specific task, functional data will be
1085 convolved to an event-related or boxcar waveform based on the experimental design and the canonical
1086 hemodynamic response function. Artifact detection will be conducted with the Artifact Detection Tool
1087 (ART) program. Images with global intensities exceeding 3 standard deviations or scan-to-scan
1088 movement exceeding 1mm will be statistically regressed out of the design matrix. For event related
1089 analyses, individual subject motion parameters will also be included as nuisance regressors in the design
1090 matrix

FMRI Statistical Analysis: At the first stage, activation during the conditions of interest will be fitted using the general linear model in SPM8 for each subject individually. This procedure yields a statistical parametric map that isolates the activity unique to the condition of interest (e.g., masked affect) relative to the activity associated with the control condition (e.g., simple perception of neutral facial expressions). Thus, for each subject, a “contrast image” will be produced that reflects the pattern of BOLD signal change due to the independent variable for each task. At the second stage, subject specific contrast images will be entered as the dependent variables in a series of random effects analyses in SPM8 [124]. Functional data will be analyzed from two approaches, including region of interest (ROI) analyses and whole brain exploratory analyses.

1. ROI Analyses. First, a series of region of interest (ROI) analyses will be performed. The primary hypotheses for the MAT involve changes in the amygdala, anterior cingulate gyrus, and ventromedial prefrontal cortex for the MAT, whereas the ACC and dorsolateral prefrontal cortex are hypothesized to differ across groups for the MSIT. Consequently, ROIs will be placed in these regions, defined according to the boundaries of the published anatomical atlas of Tzourio-Mazoyer and colleagues [125] and PickAtlas Utility [126]. These ROI analyses will be carried out at an FDR small volume corrected threshold of $p = .05$, k (extent) = 10. Each of the probe tasks has been selected because of its prior involvement in the neurocircuitry of PTSD.

1108 2. Whole Brain Exploratory Analyses. Furthermore, whole brain analyses will be undertaken to
1109 examine global patterns of activation for each of the previously described analyses. Because these
1110 analyses will be exploratory in nature, they will be evaluated at a stringent correction for multiple
1111 comparisons using a whole brain family-wise error (FWE) correction of $p < .05$, $k = 10$.

3. Resting State Functional Connectivity Analysis: Preprocessed resting state data will be analyzed using the fMRI Functional Connectivity Toolbox (CONN). Physiological and other noise sources are reduced through the implementation of a CompCor strategy implemented within the toolbox. For each subject, gray and white matter masks will be created from the previously segmented images in SPM8 and entered as nuisance covariates in the analyses, as will subject specific motion parameters. Regions of Interest (ROIs) will be created from the Automated Anatomical Labeling Atlas [125]. ROI to ROI and seed-to-voxel analyses will be run individually at the first level and then imported into a second level random effects group analysis. Primary seed regions for connectivity analyses will include the

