- All participants will be adults (age 18 to 50), thus issues regarding assent from minors are not relevant.

7) Procedures involved in the Human Research

General Procedure: Over a 4-year period, 108 participants between the ages of 18 and 50 will be recruited to participate (to reach a final n of 90 subjects, assuming 20% attrition). Participants will comprise active duty, Reserve, National Guard, or recently discharged combat-exposed military personnel or DoD contractors from Operation Enduring Freedom/Operation Iraqi Freedom (OEF/OIF) meeting DSM-V diagnostic criteria for PTSD, in addition to some non-military individuals who meet the DSM-V diagnostic criteria for PTSD. Combat-exposed individuals within 10 years of return from OIF/OEF will be eligible. An age range of 18-50 years has been selected to minimize possible developmental and degenerative effects that could be expected in younger and older subjects and to encompass the age range of the majority of military personnel.

FORM: Application for Human Research
NUMBER
FORM DATE
PAGE

F200

02/2014

23 of 44

724 Prior to data analysis, subjects who consent will have a follow-up phone call where they will be
 725 administered the PCL-5, PHQ-9, and be asked about general sleep problems using the ESS and ISI.
 726

727 The procedures will essentially be identical to those used successfully in our pilot study of patients
 728 with mTBI. Participants will attend three laboratory sessions (see Figure 10 below). Visit 1 involves
 729 informed consent, demographic data collection, and basic psychiatric assessment. Participants will be
 730 provided with a wrist actigraph sleep monitor. After a week of at home monitoring, each participant will
 731 return for Visit 2, which is involves comprehensive neurocognitive assessment, neuroimaging, fear
 732 conditioning testing, objective sleepiness monitoring and heart rate monitoring. Then participants will be
 733 randomly assigned to one of two light therapy conditions (n = 45 per group) differing only in the
 734 wavelength emitted by each light therapy device. Participants will be randomly assigned to either the BL
 735 condition or the PL condition, using computerized permuted block randomization to match groups by
 736 gender. Participants assigned to the active treatment condition will undergo 6-weeks of at-home treatment
 737 with a light device fitted with blue light (BL) diodes, while those assigned to the Placebo (PL) condition

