 1006 required to wear the wrist actigraph at all times. This device includes a light monitor that is sensitive to
 1007 various wavelengths of light. This light data will be evaluated at the conclusion of the study to identify
 1008 whether there is a detectable change in blue/red light during the period of reported light exposure.

1009 **Post-Treatment Assessment and Scan:** At the completion of 6-weeks of BL or PL, participants
 1010 will return to the imaging center for Visit 3 to complete an
 1011 identical series of assessment and neuroimaging tasks as in
 1012 Visit 2, as well as a repeated administration of the CAPS.
 1013 Participants will return wrist actigraphs and the goLITE
 1014 device.

1015 Please note that subjects will be offered and required
 1016 to wear earplugs and/or earphones to minimize the scanner
 1017 noise. Subjects will be able to converse with a staff member
 1018 via a microphone and speaker system at all times during the
 1019 scanning session. Subjects will be provided with an
 1020 emergency button to indicate an immediate concern.
 1021 Subjects may ask to have a scan stopped and discontinue
 1022 participation in the study at any time.

1023 **Follow-Up.** After subjects complete the study, prior
 1024 to data analysis, subjects will be sent an email (*Follow-up*
 1025 *Script.doc*) with a link to an online ICF Addendum
 1026 (*PTSD_ICF_addendum.doc*) and, if they agree, subjects
 1027 will complete a 10- to 15-minute follow-up online survey,
 1028 where they will be administered the PCL-5, PHQ-9, and be
 1029 asked about general sleep problems using the ESS and ISI.
 1030 If subjects cannot complete this follow-up online, follow-up
 1031 assessments will be administered over the phone.

D. DATA ANALYSIS

1034 **Global Statistical Analysis Approach:** Behavioral
 1035 data from the neurocognitive, sleep, and symptom measures
 1036 will be evaluated for clinical severity and transformed into change metrics from baseline to post-treatment
 1037 sessions. Baseline characteristics between subject groups will be examined using analysis of variance
 1038 (ANOVA) and chi-square tests, as appropriate, and randomization will be stratified by severity of PTSD

[figure not shown]

Figure 18. Power analyses show that the proposed sample size should be adequate to address the primary hypotheses.

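### Baseline adjustment is left conditional: neither the outcome's own baseline nor the randomisation strata are fixed as covariates, and the strata are described in two ways

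*Combined protocol and SAP*

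**What the plan says.** Section D, Global Statistical Analysis Approach, says that behavioural outcomes "will be evaluated for clinical severity and transformed into change metrics from baseline to post-treatment" sessions. Baseline characteristics are to be compared between groups by ANOVA and chi-square. For the primary analyses of mood and sleep, repeated "measures analysis of variance (ANOVA) and linear mixed-model approaches will be used for the primary" analyses. The only covariate statement for these models is that the between-group factors "will correspond to the two light conditions (BL vs PL) and will control for any baseline" "differences in demographic variables and severity scores as appropriate". The Power Analysis paragraph places the primary hypotheses on interaction effects ("treatment x session interactions), which will have exceptional power") in a design of two arms by two sessions.

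The strata are described twice:

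- **Section D:** "ANOVA) and chi-square tests, as appropriate, and randomization will be stratified by severity of PTSD" "and gender. Randomization will consist of permuted blocks to achieve balance over time".
- **Section 7, General Procedure:** participants go to the BL "condition or the PL condition, using computerized permuted block randomization to match groups by" gender. The section on the at-home six-week treatment repeats this, and neither mentions severity.

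Section D gives no measure or cut-point for the severity stratum. The Intake Visit text evaluates PTSD severity with the SCID. The Visit 2 and 3 text assesses it with the PCL-5, PHQ-9 and CAPS-5.

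**The concern.** For an outcome measured once at Visit 2 and once at Visit 3 with complete data, the treatment-by-session interaction is the same test as a two-sample t-test on change. A mixed model with unconstrained baseline means gives the same result. Baseline is therefore used, but with its slope fixed at 1 rather than estimated. The equivalence does not extend to daily actigraphy, the later follow-up survey or incomplete data (General Procedure assumes 20% attrition).

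Two things are at stake. The first is precision, because estimating the slope uses the same data better. The second is prespecification. Covariates enter only if differences are seen and judged to matter, so the primary model is not settled until the baseline data have been examined, and the models on offer can disagree.

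The strata raise a separate practical problem. They cannot be put in the model until the document agrees on what they are.

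**Working it through.** **Inputs from the plan.** 45 per group, N = 90, alpha .05, f = .25, and stated interaction power .99. **Assumed.** Pre-post correlation ρ (the readable text gives none), equal pre and post variances (raw SD 1), complete data, two-sided tests. The 0.5 SD effect used below is also an assumption.

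**1. The plan's own figure.** For a 2 × 2 within-between interaction, λ = f² × N × 2/(1 − ρ), on F(1, 88).

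- ρ = .3: λ = 0.0625 × 90 × 2/0.7 = 16.07, power .978.
- ρ = .5: λ = 0.0625 × 90 × 2/0.5 = 22.5, power .997, which agrees with the stated .99.

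**2. What f = .25 means.** For a between-arm difference D in change, the squared noncentrality of the t-test is D² × (45/2)/(2(1 − ρ)) = 11.25 D²/(1 − ρ). Step 1 gives λ = 11.25/(1 − ρ), so D = 1.0 raw SD.

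**3. Variance of the two analyses.** SD(change) = √(2(1 − ρ)), with 88 df. SD(ANCOVA) = √(1 − ρ²), with 87 df. The variance ratio is (1 − ρ²)/(2(1 − ρ)) = (1 + ρ)/2. Dividing 90 by this ratio gives the number of participants a change-score analysis would need for the same precision.

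**4. Power for a 0.5 SD difference (noncentral t).** At ρ = .5, the noncentrality is 0.5 × √22.5 = 2.37 for change and 2.37/√0.75 = 2.74 for ANCOVA.

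| ρ | Variance ratio | Equivalent N | Power, change | Power, ANCOVA |
|---|---|---|---|---|
| .3 | 0.65 | 138 | .509 | .691 |
| .5 | 0.75 | 120 | .650 | .773 |
| .7 | 0.85 | 106 | .857 | .907 |
| .8 | 0.90 | 100 | .960 | .974 |

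**5. The same comparison at the plan's f = .25.** Power goes from .978 to .998 at ρ = .3, and from .997 to .9997 at ρ = .5.

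**6. Conditional adjustment.** The plan states no trigger, so three were assumed: adjust for the outcome's baseline only if its between-arm test has p below .05, .20 or .50. Simulated power at 0.5 SD, 40,000 trials per cell:

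| ρ | Never | p < .05 | p < .20 | p < .50 | Always |
|---|---|---|---|---|---|
| .3 | .507 | .514 | .539 | .593 | .686 |
| .5 | .649 | .657 | .677 | .714 | .766 |
| .7 | .861 | .867 | .876 | .890 | .905 |
| .8 | .960 | .962 | .965 | .969 | .973 |

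With no true effect, the rejection rate is .049–.050 for change, .048–.051 for ANCOVA and .032–.047 for the conditional rules.

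**7. Agreement between the models.** At 0.5 SD, change score and ANCOVA give different verdicts at .05 in 24%, 17%, 7% and 2% of trials for ρ = .3, .5, .7 and .8.

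**8. Cost of stratum terms.** Three terms that explain nothing reduce ANCOVA to 84 df. At ρ = .5 and 0.5 SD, power moves from .7729 to .7725.

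**The case against.** The planned analysis is valid, and it uses baseline through the change metrics and the session factor. At the effect the plan was powered for, adjustment hardly matters: power is already .978 or higher at ρ of .3 or more, and at 1.0 SD the two models disagree in only 0.3% of trials at ρ = .5 (2.2% at ρ = .3). The larger figures need a 0.5 SD effect that the documents do not give. The conditional rules are illustrations, because no text makes a baseline p-value the trigger. The 17% disagreement is also mostly the power gain seen again: at ρ = .5, ANCOVA alone is significant in 14.5% of trials and change alone in 2.8%. The unspecified mixed model might already have a common baseline mean. The shorter account of randomisation might be incomplete rather than contradictory, since severity is assessed before allocation at the end of Visit 2.

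Most of this stands as a limit on size. The disagreement rate should not be counted as a second harm on top of lost power. It does not remove the gap. A model that might be the right one is not prespecified, and severity scores entered conditionally would not naturally cover each sleep outcome's own baseline. If the description of the strata is merely incomplete, a reader still cannot tell which factors the allocation list used.

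**Conclusion.** The concern holds, as a matter of precision and prespecification rather than validity. Under equal pre and post variances and complete data, baseline adjustment has smaller large-sample variance than the change score for any ρ below 1. The ratio is 0.65 to 0.90 over ρ of .3 to .8. How much power this buys depends on the assumed effect and ρ: about 12 points at 0.5 SD and ρ = .5, and almost nothing at the plan's f = .25. No gain is claimed from the strata terms, and no type I inflation arises under either fixed model or the conditional rules tried. The mismatch in the strata rests on the text alone and needs no assumption. This should be corrected, but it does not undermine the trial.

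**What to change.** For outcomes measured at Visits 2 and 3, prespecify one primary model: post-treatment score on arm, the baseline value of the same outcome and the randomisation strata actually used, all included whatever the observed balance. A mixed model with a common baseline mean and the same strata is an acceptable alternative, and it keeps participants who miss Visit 3. Name one of the two in advance. Report baseline characteristics descriptively, and do not use baseline comparisons to decide on adjustment.

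Make General Procedure, the at-home treatment section and section D state the same strata, namely those in the allocation list. If PTSD severity is one of them, name its measure and cut-point.

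The cost is wording and up to four degrees of freedom: one for baseline and up to three for strata, if gender and severity are crossed at two levels each (the documents give no number of severity levels). No new data are needed.
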